Study Protocol

Official Title: Remission through Early Monitored Insulin Therapy - Duration Month (REMIT-DM)

ClinicalTrials.gov ID (NCT number): NCT03670641

Protocol Date: 06 July 2021

Scientific Background

REMIT-DM is a feasibility study that aims to show that previously published diabetes remission through early use and titration of short-term insulin therapy is possible and safe in the ambulatory diverse American population of patients with T2D, with continuous glucose level and trend information provided by CGM. We developed the algorithm based on published diabetes remission studies and include within the algorithm the CGM trend arrows to further refine insulin doses for both safety and efficacy purposes. Data captured by the CGM transmits automatically to the cloud and is accessible at any time of day by the multidisciplinary diabetes team, which includes the certified diabetes educator (CDE) and Endocrinologist. The CGM-guided insulin titration algorithm is designed to achieve euglycemia (defined as fasting CBG < 100 mg/dL, and 2 hour post-prandial CBG < 120 mg/dL) within 2 weeks of initiating insulin therapy, then to help maintain euglycemia for 2 weeks before discontinuing insulin entirely. Ten subjects will undergo a maximum of 4 weeks of insulin therapy and will be assessed for remission afterwards to confirm enough recovery of beta cell function. (Complete remission is defined as fasting glycemia <100 mg/dL without use of pharmacological therapy.) Afterwards, we will implement American Diabetes Association (ADA) guidelines for standard glycemic management, as necessary. We will use the data collected during this feasibility study to sharpen the CGM-guided insulin titration algorithm for creation of a T2DM remission mobile application that could then be tested and studied in a larger sample size. The feasibility study will also take into account clinically meaningful data points e.g. the number of phone calls between the patient and the diabetes team, the patient experience, and patient satisfaction.

Study Objectives

Study Design & Methods

Participants will be assessed by the endocrinologist and diabetes educator to be able to perform skills necessary for CGM use and insulin delivery. If the CDE determines that the patient is unable or unwilling to perform the necessary care tasks, this will be communicated to the endocrinologist for potential exclusion from the study.

The Research Activities:

-Study Visit 1: The PAID-5 survey will be administered to assess diabetes distress by the RN CDE prior to the diabetes education session. Subject will undergo standard of care diabetes self-management education by the study team members, including the initiation of the CGM. OGTT lab blood draw will be done.

-Study Visit 2: Subject will undergo standard of care education for insulin start. Research activity: study team will provide the insulins and instruct the subject in the insulin titration protocol and how CGM readings will be used to manage insulin doses. Subject will adjust their meal-time insulin doses by the before meal blood sugar and the CGM predictive arrows and their daily basal insulin based on how close fasting glucose was to glucose target. Study team will confirm that subject understands how the study works using the teach-back method. Ample time for question and answer will be allotted.

-Study Visit 3: The PAID-5 will be administered at this visit as well as the satisfaction survey. These will both be administered by the RN CDE prior to the education session. If remission is achieved, patient will turn in their CGM and go off their insulin. A repeat OGTT lab blood draw will be done at this time as well. If remission is not achieved, the standard ADA algorithm would apply and patient would be placed back on their medication(s). However, there may be some patients that would prefer to stay on insulin or for which remaining on insulin therapy is

appropriate. The patient will be started on appropriate therapy as guided by clinical decision making.

-Study Visits 4-6: post 4 weeks-1 year patient will have standard of care endocrinology visits driven by clinical decision making.

-Study Visit 7: At 12 months, the PAID-5 and satisfaction survey will again be administered by the RN CDE.

Algorithm Development/Data Analysis Period:

-Post 12 month intervention period: Algorithm and Protocol development

All program data, e.g. number of calls, length of calls, information reviewed/requested on call, documentation of extraneous calls, e.g. after hours/outside of schedule. Clinical outcomes, e.g. rates of hypoglycemia, laboratory results will be analyzed and reviewed. Based on the findings a full protocol that includes the finalized insulin titration algorithm and program processes will be prepared.

Eligibility Criteria

Inclusion criteria:

- Age ≥ 18
- A1C criteria - >7.0
- Diagnosed with T2D within 4 years
- Lifestyle controlled
- Subject may be on up to 2 medications for diabetes.
- Smart phone or home computer compatible with DEXCOM CLARITY software
- English speaking
- Assessed by endocrinologist and diabetes educator to be able to perform skills necessary for CGM use and insulin delivery

Exclusion criteria:

- Autoimmune Type 1 DM, defined as positive GAD65 or islet cell antibodies
- Pregnant
- Chronic Kidney Disease (CKD) Stage IV or greater
- Mental and/or cognitive disorder (based on documented disorder and/or assessment of physician or educator)
- No access to computer for downloading CGM
- BMI <18.0

Statistical Considerations

This is a feasibility study that does not require power calculation.

Baseline characteristics will be described using measures of central tendencies (means, median, standard deviations). To examine time to glucose target range, hypo/and hyperglycemia, logistic regression will be used. Covariates in the models will include demographic factors, glucose dosing information, insulin protocol used.

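### Ten subjects can show that remission is possible but not that the approach is safe; restate the aim as estimation and report remission and hypoglycemia as x/n with exact intervals

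*Combined protocol and SAP*

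**What the plan says.** The aim is in the Scientific Background: "REMIT-DM is a feasibility study that aims to show that previously published diabetes remission" by early short-term insulin "is possible and safe in the ambulatory diverse American population" of patients with type 2 diabetes. The same section sets the size and exposure: "Ten subjects will undergo a maximum of 4 weeks of insulin therapy". No comparator or randomisation is described. The section also defines complete remission (fasting glucose below 100 mg/dL without drug treatment). The data are to refine the titration algorithm for a mobile application "that could then be tested and studied in a larger sample size".

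Under Algorithm Development/Data Analysis Period the plan says: "Clinical outcomes, e.g. rates of hypoglycemia, laboratory results will be analyzed and reviewed". Statistical Considerations opens with "This is a feasibility study that does not require power calculation" and then says: "To examine time to glucose target range, hypo/and hyperglycemia, logistic regression will be used". The covariates are demographic factors, glucose dosing information and the insulin protocol used.

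The plan states no acceptable event rate, precision target or confidence interval, and it names no analysis for the proportion in remission.

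**The concern.** The two halves of the aim need different evidence. That remission is possible is an existence statement, and a few remissions among ten subjects can support it. That the approach is safe in a diverse outpatient population is a statement about an upper bound on risk, and ten subjects cannot bound risk tightly.

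The planned analysis does not make this limit visible. Nothing in it puts a count over a denominator with an interval. The result most likely to be read as safe, no subject with an event, is also one that the named model cannot quantify at subject level. A reader could take a clean result as a demonstration, when the data would still be compatible with a substantial risk. This matters because subjects adjust their own insulin at home, and because the findings feed the finalised algorithm and a fuller protocol.

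**Working it through.** The plan derives no figure for ten subjects, so there is nothing to reproduce. The check asks what ten subjects can exclude.

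**Inputs.** n = 10 and at most 4 weeks of insulin, both from the Scientific Background. The plan sets no confidence level, so 95% is assumed. All event counts and true risks below are assumptions for illustration. An event means any yes/no outcome per subject, such as at least one hypoglycemic episode under whatever definition the study adopts.

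**No subject with an event.** The exact upper limit solves (1 − p)^n = α/2 (two-sided) or α (one-sided):
- Two-sided 95%: 1 − 0.025^(1/10) = 1 − 0.6915 = 30.8%.
- One-sided 95%: 1 − 0.05^(1/10) = 1 − 0.7411 = 25.9%.
- Other methods agree closely: the rule of three gives 3/10 = 30%, and the Wilson two-sided limit is 27.8%.
- If only 9 or 8 subjects were evaluable, the exact two-sided limit would be 33.6% or 36.9%.

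**Chance of a clean result when the risk is real.** P(no event) = (1 − p)^10:

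| Assumed true risk per subject | P(0 of 10) |
|---|---|
| 1% | 90% |
| 5% | 60% |
| 10% | 35% |
| 20% | 11% |

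**A few events.** The exact two-sided 95% interval is 0.3% to 44.5% for 1/10 and 2.5% to 55.6% for 2/10.

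**Events per unit time.** If all ten subjects complete 4 weeks, exposure is 10 × 4/52 = 0.77 subject-years. With zero events and a Poisson assumption, the two-sided upper limit is −ln(0.025)/0.769 = 3.689/0.769 = 4.8 events per subject-year. This scale is no more reassuring.

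**Remission.** For 5/10, the Clopper-Pearson limits are the 2.5% point of Beta(5, 6) and the 97.5% point of Beta(6, 5), which gives 18.7% to 81.3%.

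**Scale of a safety demonstration.** The smallest n at which zero events brings the limit down to p is ln(α/2)/ln(1 − p), rounded up. For 10% this is 36 subjects two-sided (29 one-sided, with α in place of α/2). For 5% it is 72 (59 one-sided). These figures show the gap between the aim and the design; they are not a proposed sample size.

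**The named model.** In a logistic model with an intercept, the maximum-likelihood fit makes the fitted probabilities sum to the number of events. With zero events every fitted probability would have to be zero, so the intercept goes to minus infinity and no finite estimate exists. The same failure occurs if all ten subjects have an event. Between these extremes, the three named covariate groups need at least three coefficients plus an intercept. That is at least four parameters from ten subjects, with at most five in the rarer outcome class.

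**The case against.** The strongest reply is that this is openly a feasibility study, and much of that stands. Ten subjects without a power calculation are acceptable for that purpose. The sentence at issue is in a background section, and no hypothesis, margin or success rule for safety appears, so a clean result triggers no formal decision. The Study Objectives heading has no text under it in the available copy, which may be an extraction loss, so a more modest formal objective may exist. The protocol also foresees testing the application in a larger sample and preparing a full protocol first.

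A reader might infer that the plan has no safety analysis. The documents do not support this: hypoglycemia rates are to be reviewed, and hypoglycemia is named in the logistic regression. What is missing is a stated proportion, denominator and interval. A reader might also infer that the study needs more subjects, or that its data lead straight to deployment of the application. Neither follows, because n = 10 suits feasibility and the stated next step is further study.

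It is also fair that the protocol does not define a serious event and that the 0/10 and 5/10 outcomes are hypothetical. A per-subject proportion is not the only summary that continuous glucose data allow. The lack of a comparator does not enter the 30.8% limit, which depends only on n and the count.

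None of this removes the mismatch between aiming to show safety and a design that can only describe it. The planned larger study is a reason to call the present safety information preliminary.

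**Conclusion.** The concern holds as a matter of wording and reporting. The design supports the statement that remission is possible; it does not support a conclusion that the approach is safe in the stated population. On the illustrative assumption of no subject with an event, risks up to 30.8% (exact two-sided 95%) or 25.9% (one-sided) remain compatible with the data, and every method tried gives a limit between about 26% and 31%. These are limits on what could be excluded. They are not estimates of risk, and they do not suggest that the treatment is unsafe. They assume independent subjects and a yes/no event per subject, with all ten evaluable.

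The analysis gap is specific: remission has no stated analysis, and hypoglycemia has a model but no x/n with an interval. The statement about model failure applies to a subject-level outcome. The plan does not name the unit of analysis.

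**What to change.** 1. In the Scientific Background, and in Study Objectives if they repeat it, restate the aim as estimating feasibility, the proportion in remission and the frequency of hypoglycemia. Describe safety as preliminary, pending the larger study that the protocol foresees.
2. In Statistical Considerations, make the main summary the proportion of subjects in remission and the proportion with hypoglycemia. Report each as x/n with an exact (Clopper-Pearson) 95% interval, and put all subjects who start insulin in the denominator. State the event definition, the time point for remission and how a subject who stops early is counted; the clinical definitions are for the investigators to set.
3. Do not rely on the multi-covariate logistic model for these outcomes. If it is kept, label it exploratory and name its unit of analysis.

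The statement of what an observed count does not exclude belongs in the results report, once the count is known.

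The cost is a more modest claim and a few sentences of protocol text. No extra subjects, visits or data are needed, and no clinical rule changes.

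### Does a glucose target with upper limits only let over-lowering count as success in the time-to-target analysis?

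*Combined protocol and SAP*

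**What the plan says.** The document gives one numeric on-treatment target. In Scientific Background the algorithm is designed to achieve "euglycemia (defined as fasting CBG < 100 mg/dL, and 2 hour post-prandial CBG < 120 mg/dL" mg/dL, and to do so "within 2 weeks of initiating insulin therapy, then to help maintain euglycemia for 2 weeks before discontinuing insulin entirely". Both parts are upper limits. The only other glucose threshold in the document is for the off-treatment period: "Complete remission is defined as fasting glycemia <100 mg/dL without use of pharmacological therapy".

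The analysis is described in Statistical Considerations: "To examine time to glucose target range, hypo/and hyperglycemia, logistic regression will be used". No limits are given there for the target range, for hypoglycemia or for hyperglycemia, and the sentence does not refer back to the euglycemia definition.

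Under Algorithm Development/Data Analysis Period, hypoglycemia is also reviewed as an outcome in its own right: "Clinical outcomes, e.g. rates of hypoglycemia, laboratory results will be analyzed and reviewed". The results then feed the next stage: "Based on the findings a full protocol that includes the finalized insulin titration algorithm and program processes will be prepared".

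**The concern.** An analyst who needs limits for the target range will look for numbers, and the euglycemia definition is the only on-treatment candidate. Used as a scoring rule it runs one way. A hypoglycemic fasting value always meets the fasting part, and a hypoglycemic post-prandial value always meets the post-prandial part. A day on which both are low counts as euglycemia. More aggressive lowering would then shorten the measured time to target, and the same day could be counted both as a success and as hypoglycemia.

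This would matter because the study sets out to show that the approach "is possible and safe in the ambulatory diverse American population of patients with T2D" and because its findings shape an insulin titration algorithm. A score that cannot separate good control from over-lowering would be a poor guide for that purpose.

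**Working it through.** The plan states no power, error rate, effect size or derived figure, so there is nothing of its own to reproduce. Three checks apply.

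**1. Is the rule one-directional?** Input: the euglycemia definition (fasting F < 100 and post-prandial P < 120 mg/dL). Applied to F/P pairs, 95/115 passes, 105/115 fails, and 65/110, 50/60 and 40/45 all pass. Over all integer pairs from 40 to 199 mg/dL, lowering a reading by one unit never turned a pass into a fail (0 violations). So for the scored readings, lower glucose improves the score or leaves it unchanged. The check does not cover a rebound high after a low, which could fail a later reading.

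**2. How large is the effect on the named outcome, time to target?** The document gives no glucose means, SDs, readings per day or hypoglycemia cut-off, so every input here is an assumption: independent normal values, SD 15 (fasting) and 20 (post-prandial), cut-off 70 mg/dL, and k post-prandial readings a day.

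- Daily pass probability as written: p = Φ((100 − mF)/15) × Φ((120 − mP)/20)^k.
- With values below 70 excluded: subtract Φ((70 − mF)/15) from the first factor, and Φ((70 − mP)/20) from the second before raising it to the power k.
- Means fall linearly from 160/220 to the final values over 14 days, then stay flat. The mean first target day, restricted to day 28, is the sum over d = 1 to 28 of the probability that no earlier day passed.

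| Final means F/P | k | As written | Lows excluded | Delay (days) |
|---|---|---|---|---|
| 95/110 | 1 | 13.88 | 14.08 | 0.20 |
| 80/100 | 1 | 12.07 | 12.38 | 0.31 |
| 70/90 | 1 | 11.10 | 11.57 | 0.47 |
| 95/110 | 3 | 17.13 | 17.85 | 0.72 |
| 80/100 | 3 | 13.88 | 15.01 | 1.13 |
| 70/90 | 3 | 12.70 | 14.65 | 1.95 |

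The delay is 0.2 to 2.0 days. The lowest-glucose scenario stays fastest after the exclusion for both values of k, so on this outcome the exclusion does not reverse the ordering.

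**3. How large is the effect on days at target?** This is 14 × p at the final means. For 70/90 with k = 1, as written: 14 × Φ(2.0) × Φ(1.5) = 14 × 0.9772 × 0.9332 = 12.77. With lows excluded: 14 × (0.9772 − 0.5000) × (0.9332 − 0.1587) = 5.18.

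| SD F/P | k | 95/110 | 80/100 | 70/90 |
|---|---|---|---|---|
| 15/20, as written | 1 | 6.10 | 10.70 | 12.77 |
| 15/20, lows excluded | 1 | 5.46 | 7.12 | 5.18 |
| 15/20, lows excluded | 2 | 3.65 | 5.51 | 4.01 |
| 15/20, lows excluded | 3 | 2.44 | 4.27 | 3.10 |
| 20/20, lows excluded | 1 | 4.62 | 5.78 | 4.70 |

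The drop for the lowest glucose is large, and it loses first place in every row with the exclusion. It becomes the worst of the three only with one post-prandial reading at SD 15/20, and then by 5.46 − 5.18 = 0.28 days. With two or three readings, or at SD 20/20, the highest glucose is worst. More to the point, Statistical Considerations does not name days at target as an outcome. Holding euglycemia for two weeks is an aim of the design.

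**The case for a change.** The best case for acting is that a sentence or two would settle the matter at no cost in data. The target range needs limits from somewhere, and the euglycemia definition is the only on-treatment source. Separate reporting of hypoglycemia exposes overshoot but does not correct the target result itself. Two weeks of maintained euglycemia is a stated goal, so someone will probably count those days. With ten subjects, a few misclassified days could be visible.

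Part of this stands. The limits of the range and the hypoglycemia cut-off are not stated, and the scoring logic is right if the definition is used literally. But the definition appears in a sentence about what the algorithm is designed to do, and no section makes it an endpoint rule. The word range suggests two bounds, and hypo- and hyperglycemia stand next to it in the same sentence. An analyst who classes each reading as low, in range or high follows that sentence at least as faithfully, and then no low value counts as on target. The large figures arise only for an outcome that the analysis section does not list.

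**Conclusion.** No change to the plan follows. The concern describes a real property of the euglycemia definition, but it becomes a bias only if that definition is taken as the scoring rule, which the document does not say and its analysis sentence does not favour. On the outcome actually named, the consequence is 0.2 to 2.0 days in the mean first target day, and excluding lows leaves the lowest-glucose scenario fastest. Those figures rest wholly on assumed means, SDs, readings per day and a 70 mg/dL cut-off, none of which the document supplies.

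What survives is a gap in detail: the target range and hypoglycemia have no stated limits. In a feasibility study of ten subjects, with no power calculation and no comparator described, analysts can settle those definitions sensibly when the data are summarised. Hypoglycemia rates are reviewed as an outcome of their own, so over-lowering would be seen when the algorithm is finalised. The choice of clinical limits belongs to the sponsor.

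### Study Visit 3 judges remission before insulin is stopped, although remission is defined as an off-drug state and no off-insulin glucose is scheduled

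*Combined protocol and SAP*

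**What the plan says.** The Scientific Background gives the definition: "Complete remission is defined as fasting glycemia <100 mg/dL without use of pharmacological therapy". It also gives an order of events. The algorithm is to bring participants to euglycemia and "maintain euglycemia for 2 weeks before discontinuing insulin entirely". Ten participants receive at most 4 weeks of insulin and "will be assessed for remission afterwards to confirm enough recovery of beta cell function". No visit, day or interval off insulin is attached to that assessment. Euglycemia during insulin treatment is "defined as fasting CBG < 100 mg/dL, and 2 hour post-prandial CBG < 120 mg/dL".

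Study Visit 3, under The Research Activities, is the only visit that mentions a remission judgement. Its rule is "If remission is achieved, patient will turn in their CGM and go off their insulin". For participants not in remission, it returns them to their previous medication under the ADA algorithm, but adds that "there may be some patients that would prefer to stay on insulin" or may need to remain on it. On laboratory testing it says "A repeat OGTT lab blood draw will be done at this time as well", without stating whether insulin has been held or whether this test decides remission.

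Visits 4-6 are routine endocrinology visits led by clinical need. Visit 7, at 12 months, lists the PAID-5 and the satisfaction survey. Statistical Considerations names no analysis of remission.

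**The concern.** The background section and the visit instruction put the same two events in opposite order. In the background, insulin stops and remission is then assessed. At Visit 3, remission is assessed and insulin then stops if the answer is yes. Under the protocol's own definition the second order cannot work, because being off drugs is part of what is being assessed.

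The shared fasting cut-off makes this more than loose wording. At Visit 2 participants are taught to adjust basal insulin daily according to how close fasting glucose is to target. They are therefore titrated towards the same number that would be read as remission.

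The stated aim is to show that remission through short-term insulin is possible and safe. If Visit 3 is followed as written, the study would report how many participants reached target on insulin under the name of remission. The repeat OGTT has a related problem: if injected insulin is still acting, the change from Visit 1 mixes its effect with beta-cell recovery. The study's data are then to be reviewed in preparing a full protocol.

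**Working it through.** The plan gives no power, alpha, effect size or target remission rate, so there is no figure of its own to reproduce. The check compares the texts, then bounds the consequence.

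**Step 1: the two criteria side by side**

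| | Drug status | Fasting cut-off | Source |
|---|---|---|---|
| Complete remission | off all drugs | <100 mg/dL | Scientific Background |
| Euglycemia (titration target) | on insulin | <100 mg/dL, plus 2-hour post-prandial <120 mg/dL | Scientific Background |

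The fasting cut-offs are identical, so only drug status separates the two states. A fasting value judged before insulin stops meets the numerical limit of both.

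**Step 2: insulin status when Visit 3 judges remission.** Stopping insulin is the consequence of a positive judgement, so insulin is still running when the judgement is made. The reference to patients who prefer to stay on insulin supports this reading.

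**Step 3: search for a later off-insulin value**

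- Visit 1: OGTT, before study insulin.
- Visit 2: insulin start; no laboratory glucose named.
- Visit 3: repeat OGTT; insulin status and interval not stated.
- Visits 4-6: no test specified.
- Visit 7: surveys only.
- CGM: returned at the point insulin stops.

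A glucose test is named at 2 of 7 visits. A glucose at a stated interval off insulin is specified at 0 of 7.

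**Step 4: bound on the remission count.** With n = 10, one participant is 1/10 = 10 percentage points. If k participants are labelled in remission while on insulin and no off-drug value exists, the number of those who meet the definition can be anything from 0 to k. For assumed values of k:

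- k = 4: 0/10 to 4/10, or 0-40%
- k = 6: 0/10 to 6/10, or 0-60%
- k = 8: 0/10 to 8/10, or 0-80%

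**Step 5: illustration with assumed rates.** Let pT be the share at fasting target on insulin and q the share of those still below 100 mg/dL once off it. Neither is in the documents. The Visit 3 rule counts n × pT; the definition counts n × pT × q.

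| pT | Visit 3 rule | q = 0.3 | q = 0.5 | q = 0.7 | q = 1.0 |
|---|---|---|---|---|---|
| 0.8 | 10 × 0.8 = 8.0 | 2.4 | 4.0 | 5.6 | 8.0 |
| 0.9 | 10 × 0.9 = 9.0 | 2.7 | 4.5 | 6.3 | 9.0 |

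The Visit 3 count does not change with q, although q is what the study needs to learn. The two counts agree only when q = 1.

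**The case against.** The strongest reply is that the correct rule is already in the protocol. The Scientific Background has insulin discontinued and remission assessed afterwards, off drugs, so anyone applying that definition could not count an on-insulin value. On this view Visit 3 is merely ambiguous. The phrase about staying on insulin sits in the non-remission branch, and the same branch speaks of starting appropriate therapy, which could suggest that participants are on none. The OGTT sentence follows the one about going off insulin, so that draw might be off insulin, and its fasting sample could then serve. Laboratory results from routine visits are also to be reviewed. Finally, this is a ten-person feasibility study whose statistical section models time to target, hypoglycemia and hyperglycemia, none of which depends on the Visit 3 rule.

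Part of this stands. The definition is right, and the insulin status of the Visit 3 OGTT is unstated rather than shown to be on insulin. A glucose is drawn at that visit; what is missing is any designation that it is off insulin. The 0-to-k range is a logical bound on assumed k, and it would not apply if the OGTT were drawn after an adequate interval off insulin. The titration, hypoglycemia and call data remain useful either way.

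The rest does not rescue the rule. An OGTT at the visit where insulin stops has no stated interval off it, and staff will follow the visit instruction. Values from routine care would depend on what each clinician ordered, with no common timing and no assurance of one for all ten participants. The absence of a power calculation is not the complaint: remission is the stated aim, and its label has to mean what the protocol says it means.

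**Conclusion.** The concern holds. As written, the Visit 3 rule judges an off-drug state before the drug is stopped, using the same fasting limit as on-insulin titration, and no later step supplies an off-insulin value at a stated time. A remission count made by that rule cannot be separated from glucose control on insulin.

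Each mislabelled participant shifts the rate by 10 percentage points, and k labelled participants are compatible with 0 to k true remissions. This is a bound, not an estimate of error, and it rests on Visit 3 being followed literally. The direction of the fault and the missing off-insulin interval come from the text and need no assumed rate. The rule should be corrected before any remission figure from this study is reported or used in planning the next one.

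**What to change.** 1. Reword Visit 3 so that insulin is stopped, where the investigator judges it safe, before remission is assessed. Report any value taken on insulin as fasting target met on insulin.
2. Count complete remission only from a fasting glucose taken off all glucose-lowering drugs, at one fixed interval after the last insulin dose that is the same for everyone. The investigator sets the interval, for example 7 days; it must exceed the duration of action of the basal insulin supplied.
3. Take the already planned repeat OGTT at that same point, and let participants keep the CGM until then.
4. Count participants who cannot stop drug therapy as not in remission. Show them as a separate number, since they have no off-drug value, and leave them out of the off-drug OGTT comparison.
5. As a smaller related point, record drug status at the Visit 1 OGTT and show it beside the OGTT change, because the Inclusion criteria allow up to two diabetes medications at entry.

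The cost is a change to the Visit 3 text, at most ten re-timed draws or short extra visits, and slightly longer CGM wear. The drug-free interval needs clinical cover, and the reported remission rate will probably be lower.

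### Time to target glucose is assigned to covariate-adjusted logistic regression with no person-day layout described; fitted in the usual way, the model does not estimate how quickly target was reached

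*Combined protocol and SAP*

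**What the plan says.** The Statistical Considerations section of the combined protocol and SAP has one sentence on outcome analysis: "To examine time to glucose target range, hypo/and hyperglycemia, logistic regression will be used". The next adds: "Covariates in the models will include demographic factors, glucose dosing information, insulin protocol used". The section also states: "This is a feasibility study that does not require power calculation".

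The context is in Scientific Background. The sample and the treatment window are given as "Ten subjects will undergo a maximum of 4 weeks of insulin therapy". The algorithm aims for euglycemia "within 2 weeks of initiating insulin therapy, then to help maintain euglycemia for 2 weeks before discontinuing insulin entirely", with euglycemia "defined as fasting CBG < 100 mg/dL, and 2 hour post-prandial CBG < 120 mg/dL". On use of the results: "We will use the data collected during this feasibility study to sharpen the CGM-guided insulin titration algorithm".

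Nowhere do the documents name a cut-off day for the logistic model, a record per participant per day, a time-to-event method, or a rule for participants who stop early or never reach target. The statistics section does not link its model to the 2-week goal or to the 4-week maximum.

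**The concern.** The outcome named is a duration, and the method named is for a yes/no outcome. Logistic regression with one row per participant needs the duration reduced to whether target was reached by some day. Three things follow:

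- The day has to be chosen, and the section does not choose it.
- Everyone who reached target by that day is treated alike, whether on day 2 or day 14.
- A participant who stops before that day without reaching target is neither a yes nor a no. One who stops after it without reaching target is a known no.

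The study's product is a refined titration algorithm designed to bring glucose to target within 2 weeks. How early in that window each participant gets there is direct evidence on titration, and a yes/no model drops it.

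**Working it through.** The plan states no power, alpha or sample-size calculation, so there is no figure of its own to reproduce. From the documents: n = 10; goal 2 × 7 = 14 days; maximum 4 × 7 = 28 days on insulin; and the three named kinds of covariate. The individual times, early stops, success rates and covariate distributions below are assumptions, because the documents give none of them.

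**1. Timing lost.** Take two assumed sets of ten times to target, in days:

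| Set | Times | By day 7 | By day 14 | Median |
|---|---|---|---|---|
| A | 2, 3, 3, 4, 4, 5, 6, 18, 22, never | 7/10 | 7/10 | (4 + 5)/2 = 4.5 |
| B | 9, 10, 11, 12, 13, 13, 14, 18, 22, never | 0/10 | 7/10 | (13 + 13)/2 = 13 |

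With a day-14 outcome, if the same seven people reach target, the outcome data given to the model are identical. With a day-7 outcome the sets are as far apart as 7/10 and 0/10. The answer therefore turns on the unstated day.

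**2. Early stop.** In set B, let the tenth person stop at day 11 without reaching target.

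- Scored as not reached, the day-14 proportion is 7/10 = 70%. Scored as reached, it is 8/10 = 80%.
- Kaplan-Meier, proportion not yet at target: 0.9, 0.8 and 0.7 after days 9, 10 and 11, with six then at risk. Day 12: 0.7 × 5/6 = 0.583. Day 13: × 3/5 = 0.350. Day 14: × 2/3 = 0.233. So 1 − 0.233 = 77% have reached target.
- If the stop is at day 20 instead, the day-14 result is 70% with no ambiguity.

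**3. Secondary point: number of covariates.** Demographic factors (plural, so at least 2) plus dosing (at least 1) give at least 3 coefficients, even if all ten share one insulin protocol. The smaller outcome group is at most 5, so if these are entered jointly there are at most 5/3 = 1.7 outcomes per coefficient.

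For the chance that maximum likelihood has no finite solution, assume covariates unrelated to outcome and exponential times with medians of 14, 10 or 7 days. Then P(reached by day 14) = 1 − exp(−ln 2 × 14/median) = 50%, 62% or 75%.

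- Three continuous covariates at 50%: separable labellings = 2 × (1 + 9 + 36 + 84) = 260 of 2^10 = 1024, or 25.4%.
- By simulation with a linear-programming separation check, across 50% to 75%: about 25% to 45% with three normal covariates, about 57% to 73% with three binary covariates split 5/5, and only about 2% to 12% with a single normal covariate.

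**4. Precision of the simpler summary.** The exact (Clopper-Pearson) 95% interval for 7/10 is 35% to 93%.

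**The case against.** The strongest reply is that one row per participant is itself an assumption. Under the study visits, meal-time doses are adjusted by each pre-meal reading and basal insulin daily. Dosing is a listed covariate, and hypo- and hyperglycemia can recur, so daily or reading-level records would suit these features at least as well. That stands as far as it goes: the layout is unspecified, which is why the point is framed as what follows from the usual fit. It does not rescue the plan. Daily at-target status could give up to 10 × 28 = 280 clustered rows, but it describes the share of days at target, not the time to first reaching it. A person-day model that ends at first target, with a term for day, would be valid. It is not described, and it would have at most ten events for at least 3 + 1 = 4 coefficients, or 2.5 per coefficient.

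A second reply is that day 14 is implied by the 2-week goal, or that a cut-point stands under Study Objectives. No text appears under that heading in the version read, and nothing is inferred from that. A cut-point would settle the day and make a clear yes/no outcome relevant to the goal. It would still not be the time outcome that the statistics section names.

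Third, the harm is modest. The study has ten participants and no stated test, alpha or success rule. The team will review clinical outcomes when finalising the algorithm and can look at the ten times directly. This is correct, and it limits severity. It does not make the named analysis fit the named outcome.

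Finally, the separation percentages depend on entering three covariates jointly. The plan speaks of models in the plural and gives no number of terms per model. That also stands, so those figures are secondary support only.

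**Conclusion.** The point holds in a limited form. As written, the plan pairs a time outcome with a method that, fitted in the usual way, does not estimate time, and it describes no layout under which it would. The 4.5-day versus 13-day contrast shows what can be hidden behind the same 7/10; it rests on invented times and is not a forecast.

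A reader might infer more, and the documents do not support it:

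- *That logistic regression can never analyse a time.* It can, on person-day records.
- *That the model will fail to fit.* This depends on the number and type of covariates and on the success rate, none of which is given.
- *That a study conclusion is invalidated.* No power, test or decision rule hangs on this analysis; the loss is descriptive information for refining the algorithm.
- *That the hypo- and hyperglycemia analyses share the fault.* They are named in the same sentence, but this point covers time to target only.

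Severity is minor to should-fix: the consequence is limited, but the mismatch is plain and cheap to remove.

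**What to change.** For time to target only, replace the logistic model with:

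1. A listing of the ten individual times, with the reason for any early stop.
2. A Kaplan-Meier estimate from first insulin dose to first reaching target, censored at end of study insulin or at withdrawal. Report the median and the proportion at target by day 14 with a 95% interval, exact binomial if nobody is censored before day 14.
3. If anyone stops before day 14 without reaching target, the day-14 proportion with all such people counted as not reached, and again with all counted as reached.
4. A sponsor statement of the event: the euglycemia definition in Scientific Background, or another definition based on readings the study collects. It should make clear what counts as first reaching target, since the protocol separates achieving euglycemia from maintaining it.

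The cost is one short paragraph in the statistics section plus the event definition; no added visits or participants are needed. The downsides are wide intervals, reliance on early stopping being non-informative (each stop before day 14 without reaching target widens the gap between the two bounds by 1/10, or 10 percentage points), and no covariate-adjusted model for this outcome. With ten participants, little is lost by giving that up.
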